4.1 Screening Data, Eligibility and Recruitment

Clubs will be eligible for participation if they are able to participate with one club leader, 2-6 teams (teams from at least two different age groups (13-17) and both the boy and girl league should ideally be represented), and a minimum of one coach from each of the participating teams.

A CONSORT flow diagram (18) will be used to summarize the number of participants who were:

- Included and randomised
- Received the intervention
- Lost to follow-up (reasons will be provided)
- Randomised and included in the primary analysis

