5.2.1 Primary Outcome

Analysis

The primary outcome (weekly injury severity score) will be analyzed with a linear mixed model. The model will include fixed effects for intervention (intervention vs control), time point, intervention x time point interaction, and geographical region (stratification factor in the randomisation). Time point is defined as 1 for the first response to the OSTRC questionnaire (week 42, 2024), 2 for the second response to the questionnaire (week 44, 2024), and so on until 13 for the last response (week 14, 2025). The model will include random intercepts for players nested within clubs. The predicted margins over all time points will be presented for intervention and control separately with 95% confidence intervals (CIs). The effect measure will be the difference between the weekly injury severity score for intervention and control, estimated as the predicted marginal effect of intervention over all time points, based on the fitted linear mixed model. The effect estimate will be presented with a 95% CI and a P-value for the null hypothesis of a difference equal to zero.

The predicted margins for intervention and control will be presented with 95% CIs for each time point in a plot. The estimated intervention effect (difference between intervention and control) with a 95% CI for each time point will also be shown in a plot.

Assumption checks

The distribution of the primary outcome (injury severity score) will be assessed with descriptive statistics and histograms. With a sample size of approximately 2000, the linear mixed model will be robust to quite large deviations from the normal distribution, and the injury severity score is bounded below at 0 and above at 100, so its distribution cannot be severely skewed. Still, in the unlikely case that the distribution of the outcome is deemed to deviate too much from the normal distribution, a log transformation of the outcome will be done prior to fitting the linear mixed model. In that case, an analysis of the untransformed data will be performed as an additional sensitivity analysis. After fitting the model (original scale or log transformed), plots of observed and model-fitted values (by intervention group and time point) will be compared to assess the fit of the model.

Missing data

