The linear mixed model will handle missing data in one or more time points per player under the assumption of missing at random. No patient in the FAS has missing data on all fourteen time points, per the definition of FAS (see section 3.3).

Subgroup analysis

A subgroup analysis of the primary outcome will be performed by team gender. The analysis will be as described for the primary analysis of the primary outcome above; however, instead of an interaction term between intervention and time point, there will be a three-way interaction between intervention, time point, and team gender. The results will be a separate estimated intervention effect across all time points for each team gender and separate plots of estimated intervention effects for each time point for each team gender. No hypothesis tests for intervention effects will be performed.

STATISTICAL ANALYSIS PLAN for Effectiveness of the Injury-preventive Program #Utviklingsklar

A test for subgroup effect (i.e. a test for the null hypothesis of equal intervention effects for each team gender) will be calculated with a likelihood ratio test for the models with and without interaction by team gender.

Sensitivity analyses

The following sensitivity analyses will be performed for the primary outcome:

- Analysis restricted to the first part of the season (2024, time point 1-6)
- Analysis restricted to the second part of the season (2025, time point 7-14)
- Analysis on untransformed data (only if the primary analysis is done on log-transformed data)

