5.2.5 Ordinal Secondary Outcomes

Analysis

STATISTICAL ANALYSIS PLAN for Effectiveness of the Injury-preventive Program #Utviklingsklar

The ordinal secondary outcomes on coach practices are measured as the change in an ordinal 7-point scale from baseline to end of season. The change (baseline minus end of season) will be an outcome ranging from -6 (score 1 at baseline and 7 at end of season) to 6 (score 7 at baseline and 1 at end of season). This outcome is an ordinal outcome with 13 categories. With approximately 120 coaches, many of the categories will be sparsely populated, and we believe that an ordinal regression model would be a poor choice with these many categories and so few data. Instead, we will compare the mean number of categories of change from baseline to end of season for intervention vs. control. The outcomes will be analyzed with linear regression models with intervention (intervention vs control) and geographical region (stratification factor in the randomisation) as the explanatory variables. The standard errors will be adjusted to account for clustering within clubs. Based on the fitted model, the predicted margins for intervention and control separately and the predicted marginal effect of intervention will be presented with 95% CIs. The observed counts (and percentages) on the original 13-point ordinal scale will be presented for intervention and control.

Assumption checks

The distributions of the residuals from the fitted linear regression models will be assessed with descriptive statistics and histograms. With only 13 possible outcomes, it is very unlikely that the distribution of the residuals will exhibit any signs of large deviations from the normal distributions. Still, in the case that the distribution of the outcome is deemed to deviate too much from the normal distribution, a log transformation of the outcome will be done prior to fitting the model.

Missing data

The main analysis of the ordinal secondary outcomes will be performed on the complete case sample. As a sensitivity analysis, we will impute missing data with multiple imputation. The imputation model will be multinomial logistic regression, stratified by intervention/control, and it will include the following explanatory variables:

- Age level (team)
- Sex (team)
- Education in injury diagnosis/treatment/prevention (coach)
- Access to health personnel (team)
- Coaching experience (coach)
- University-level coaching education (coach)

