The linear mixed model will handle missing data in one or more time points per player under the assumption of missing at random. No patient in the FAS has missing data on all 14 time points, per the definition of FAS (see section 3.3).

Subgroup analysis

A subgroup analysis of the primary outcome will be performed by team gender. The analysis will be as described for the primary analysis of the primary outcome above; however, instead of an interaction term between intervention and time point, there will be a three-way interaction between intervention, time point, and team gender. The results will be a separate estimated intervention effect across all time points for each team gender and separate plots of estimated intervention effects for each time point for each team gender. No hypothesis tests for intervention effects will be performed. A test for subgroup effect (i.e. a test for the null hypothesis of equal intervention effects for each team gender) will be calculated with a likelihood ratio test for the models with and without interaction by team gender.

Sensitivity analyses

The following sensitivity analyses will be performed for the primary outcome:

- Analysis restricted to the first part of the season (2025, time point 1-7)
- Analysis restricted to the second part of the season (2025, time point 8-14)
- Analysis on untransformed data (only if the primary analysis is done on log-transformed data)

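### The team-gender subgroup model has no team-level random intercept in either plan, so its test is somewhat anti-conservative if teams differ, and the reduced model of the test is not written out.

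*SAP*

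**What the plan says.** Section 5.2.1 of each plan analyses the weekly injury severity score with a linear mixed model. The fixed effects are intervention, time point, their interaction and region, with no gender term. On the random part it says "The model will include random intercepts for players nested within clubs".

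The subgroup analysis is the same model with one change: in place of intervention × time point, "there will be a three-way interaction between intervention, time point, and team gender". It yields "a separate estimated intervention effect across all time points for each team gender", with plots per time point. The test of effect modification is described as "a test for the null hypothesis of equal intervention effects for each team gender", to be "calculated with a likelihood ratio test for the models with and without interaction by team gender", and the football plan repeats the method: "likelihood ratio test for the models with and without interaction by team gender".

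Neither plan lists which gender terms stay in the smaller model, and neither says outright that time is a factor. Section 4.1 lets a club enter "2-6 teams (teams from at least two different age groups (13-17) and both the boy and girl league should ideally be represented", so boys' and girls' teams of several ages normally sit in one club.

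**The concern.** Two features bear on the error rate of this test.

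1. **Random structure.** The gender-by-intervention comparison is made largely between teams of the same club. A club intercept cancels out of that comparison and a player intercept treats teammates as independent given the club. If teams in a club differ for other reasons (age group, coach), that variation goes into the contrast but not into its standard error.
2. **Reduced model.** The null concerns intervention effects only. Whether the test addresses that null depends on the gender terms kept in the smaller model, and the only other model written out in section 5.2.1 contains none.

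At stake is a false signal of effect modification, or intervals for the gender-specific effects that are too narrow. This is the only test of effect modification in the plan.

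**Working it through.** **Inputs.** SAP section 2.3: 64 players per club, 13 clubs per arm needed, 15 to be recruited, SD 30, club ICC 0.05, difference 8.5 (34 against 25.5). Section 5.1.2: 13 time points (handball), 14 (football). Section 5.2.5: "With approximately 120 coaches, many of the categories will be sparsely populated"; 120 coaches / 30 clubs = 4, taken as one coach per team, gives 4 teams of 64/4 = 16 players. Assumed, because the SAP gives no figure: team share of variance 1–5%, gender level difference of 2 or 4 points, half the players in girls' teams, equal team sizes, complete response, time as a factor.

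**The plan's own figure.** 2 × [30 × (1.960 + 0.842)/8.5]² ≈ 195.5 per arm; design effect 1 + 63 × 0.05 = 4.15; 195.5 × 4.15/64 = 12.7, so 13 clubs per arm. The inputs reproduce. The plan gives no figure for the subgroup test.

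**Degrees of freedom.** Intervention × time × gender has 52 cells (handball) or 56 (football).

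| Terms kept in the reduced model | df handball / football | Also tests |
|---|---|---|
| Primary model, no gender | 26 / 28 | gender, gender × time |
| Plus gender main effect | 25 / 27 | gender × time |
| Plus gender and gender × time | 13 / 14 | nothing else: the stated null |
| Only the three-way term dropped | 12 / 13 | misses a constant gender difference in effect |

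**Omitted team intercept, matching pair (13/14 df).** Take SD 30 as the SD of player averages. The within-club variance is V = 900 × (1 − 0.05) = 855. With team share s, v_t = s × 855 and v_p = 855 − v_t. With t teams of m players per club, the true variance of the contrast relative to the variance the planned model uses is

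R = (v_p + m·v_t) / (v_p + m·v_t·(t − 1)/(tm − 1)).

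- 4 × 16, s = 0.01: 983.25/852.96 = 1.153.
- 4 × 16, s = 0.05: 1496.25/844.82 = 1.771.
- 2 × 32, s = 0.05: 2180.25/833.96 = 2.614.

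Only the season-averaged component is inflated. The 1-df test therefore rejects with probability P(R·χ²₁ > 3.84), the 13-df test with P(R·χ²₁ + χ²₁₂ > 22.36), and the 14-df test likewise with χ²₁₃ and 23.68. Simulations of the likelihood ratio test agree to within about 0.2 percentage points.

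| Teams × players | Share 1% / 5%, 13 df | Share 1% / 5%, 1 df |
|---|---|---|
| 4 × 16 | 5.4% / 7.4% | 6.8% / 14.1% |
| 2 × 32 | 5.9% / 10.7% | 8.8% / 22.5% |
| 6 × 11 | 5.3% / 6.5% | 6.2% / 11.1% |

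Football's 14-df test with 4 × 16 gives 5.4% / 7.2%. With share 0, R = 1 and every entry is 5%. The standard error of the gender difference in effect is too small by √R, that is 1.07 to 1.33 for 4 × 16.

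**Primary model used as the reduced model.** With equal intervention effects and a constant gender level difference d, the noncentrality is d²/(2 × 855/n), with n = 13 × 64 = 832 or 15 × 64 = 960 per gender. For n = 960 it is 4/1.781 = 2.25 (d = 2) and 16/1.781 = 8.98 (d = 4). Rejection over the two values of n is:

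- d = 2: 8.8–9.5% (26 df), 8.6–9.3% (28 df).
- d = 4: 26.8–31.3% (26 df), 25.8–30.1% (28 df).

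**The case against.** The strongest reply is that the plan already identifies the right test. The null stands in the same sentence as the method, and a model without an interaction by gender is not a model without gender. A careful analyst would keep gender and gender × time. This largely stands: the gap in the reduced model is an ambiguity that one sentence closes. A reader might infer that the plan prescribes a test with a false rejection rate near 30%. The documents do not support that. Those rates need the literal use of the primary model, which conflicts with the stated null, and a gender difference that the SAP does not give.

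A reader might also carry over the 14–23% of the 1-df contrast at a 5% team share. That contrast is not the planned test. The planned joint test stays at 7.5% or less with 4 teams of 16, and near nominal at a 1% share.

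The team variance is itself assumed: section 2.3 gives only a club ICC. This also stands, so the inflation is conditional on teams differing. In the other direction, the football sample-size text does not say that the score is averaged per player. If SD 30 describes single weekly scores, the 13-df test with 4 teams of 16 could reach 5.6–14.8% (assumed within-player correlation 0.3–0.7).

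Finally, the analysis is supportive (section 2.4.1) and no tests within gender are planned. That is right and limits the weight of the point.

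**Conclusion.** The point holds as a minor one. The random part of the subgroup model leaves out the level at which gender varies. If teams within clubs differ, the test is somewhat anti-conservative: about 5.3–7.5% in place of 5% with 4 teams of 16, and up to about 10.7% with 2 teams of 32. The gender-specific intervals rest on the same incomplete structure. These sizes depend on the assumed 1–5% team share, time as a factor, balanced teams, complete response and SD 30 as the SD of player averages. The unwritten reduced model is a secondary matter of clarity, with a real cost only if the primary model is used literally.

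A reader might infer that the primary analysis is compromised as well. This point does not show that: clubs are randomised, the primary model has a club intercept, and the decision rule in section 2.4.2 rests on the primary null alone.

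**What to change.** In section 5.2.1 of both plans:

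- Add a random intercept for team within club to both subgroup models.
- State that time point is a factor, that gender and gender × time are in both models, and that only the terms containing intervention × gender are dropped (13 df handball, 14 df football).
- Optionally, report the gender difference in the season-averaged intervention effect with a 95% CI beside the joint test, since that average is what is shown per gender. This is a preference, not the correction of an error.

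The cost is a few sentences and one variance component. Team identity is already needed for injury burden (section 5.2.3). If teams do not differ, the test becomes slightly conservative: in simulation with 4 teams of 16, the 1-df contrast rejects in 4.5% in place of 5.0%. If they do differ, the team intercept brings that contrast to 5.1–5.3% with 4 teams of 16. With 2 teams of 32 it remains a little above nominal, at 5.5–6.1%.

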5.2.2 Repeated Measures Continuous Secondary Outcomes

Analysis

The secondary injury consequences outcomes based on the injury severity score will be analyzed in the same manner as the primary outcome, except that no hypothesis test for intervention effect will be performed.

Assumption checks

The distributions and model fit of the secondary outcomes will be explored in the same manner as for the primary outcome.

Missing data

The linear mixed model will handle missing data in one or more time points per player under the assumption of missing at random. No patient in the FAS has missing data on all fourteen time points, per the definition of FAS (see section 3.3).

5.2.3 Continuous Secondary Outcomes Measured at a Single Time Point

Analysis

Injury burden is a single-measure continuous outcome, and the unit of analysis is team. It will be analyzed with a linear regression model with intervention (intervention vs control), geographical region (stratification factor in the randomisation), and number of players per team (due to potential large variation between teams) as the explanatory variables. The standard errors will be adjusted to account for clustering within clubs. Based on the fitted model, the predicted margins for intervention and control separately and the predicted marginal effect of intervention will be presented with 95% CIs.

Assumption checks

The distribution of the residuals from the fitted linear regression model will be assessed with descriptive statistics and histograms. If the distribution of the outcome is deemed to deviate too much from the normal distribution, median regression with bootstrap confidence intervals will be used instead of linear regression. Medians and differences of medians will be reported instead of means and differences in means.

Missing data

STATISTICAL ANALYSIS PLAN for Effectiveness of the Injury-preventive Program #Utviklingsklar

Since the analysis of burden will be performed on teams as the unit of analysis, we do not expect that there are teams with missing data on burden, which would indicate that there are no data on severity score and/or exposure for any players in the team.

In cases where data are missing between two consecutive reports of the same injury, values from the preceding report should be carried forward. Consecutive reports with identical classifications for Acute/Overuse, Body Area, and Activity are considered the same injury and the incidence ID assigned to the earliest report in the sequence will be carried forward on the preceding injuries.

5.2.4 Continuous Secondary Outcomes Measured at Three Time Points

Analysis

Two secondary outcomes on coach behavioural determinants are measured at three time points (baseline, mid-season, and end of season): change in aggregated behavioral determinant scores from baseline to mid-season and change in aggregated behavioral determinant scores from baseline to end of season. A linear mixed model will be fitted to the data from all three time points. The model will include fixed effects for intervention (intervention vs control), time point, intervention x time point interaction, and geographical region (stratification factor in the randomisation). The model will include random intercepts for coaches nested within clubs. The predicted margins over all time points will be presented for intervention and control separately with 95% confidence intervals (CIs). The effect measures will be the differences between the changes in aggregated behavioral determinant scores from baseline to mid-season and from baseline to end of season for intervention vs. control. The effect estimate will be based on the predicted margins from the fitted linear mixed model.

Assumption checks

The distribution of the aggregated behavioral determinant score will be assessed with descriptive statistics and histograms. The aggregated behavioral determinant score is bounded below at 0.14 and above at 1.0, so its distribution cannot be severely skewed. Still, in the case that the distribution of the outcome is deemed to deviate too much from the normal distribution, a log transformation of the outcome will be done prior to fitting the linear mixed model. After fitting the model (original scale or log transformed), plots of observed and model-fitted values (by intervention group and time point) will be compared to assess the fit of the model.

Missing data

The linear mixed model will handle missing data in one or two time points per coach under the assumption of missing at random. For some coaches, we may have missing data for all three time points. Because we expect this to apply to very few coaches, they will be excluded from the analysis.

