2.2 Randomisation

Upon enrolment, clubs will be randomly assigned to either the control or intervention group in a 1:1 allocation ratio, using a computer-generated cluster randomisation schedule, taking differences in cluster size into account and stratified by geographical region. The biostatistician responsible for the randomisation and primary statistical analysis will be blinded to group allocation. It is impossible to blind players, coaches, and clubs to group allocation. For practical reasons (i.e., data monitoring and participant follow-up), neither the PhD students nor the principal investigator will be blinded.

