2.3 Sample size

Sample size calculation has been based on the primary endpoint (using player average weekly injury severity score during the study period of one season). Sample size estimations under varying assumptions for cluster size and effect were performed by the project biostatistician. Data from one previous study in the target population were used to estimate the average weekly injury severity score in the control group and expected standard deviation. Assuming club sizes of 64 players, 13 clubs in each trial arm are sufficient to detect a difference between the average weekly injury severity score of 34 (intervention group) and 25.5 (control group), with a pooled standard deviation of 30, 80% power, 2-tailed alpha of 0.05, and an ICC of 0.05 or less. This corresponds to a relative reduction of 25%. We will overshoot recruitment by four clubs to allow for potential withdrawal of clusters. The target number of clubs to recruit is therefore 15 in each trial arm. As cluster sizes are large, the risk of type II errors due to individual participant data loss is minor.

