2.6 Timing of Outcome Assessments

All planned measures and data collection are scheduled according to figure 1. Besides the baseline data collection, questionnaires are kept open for submission for two weeks (players) and three weeks (coaches) at each data collection timepoint. These periods are referred to as outcome assessment windows.

Activities	Participant	-1	0	T1	T2	T3
		Pre study Recruitment and consent	Pre study Baseline	Study Pre-season	Study In-season	Study Post-season
Recruitment and consent	Players, parents, coaches, club leaders	x				
Randomization	Club		x			
Quantitative data collection						
Demographics questionnaire	Players, coaches, club leaders		x			
Injury surveillance*	Players				x	
Behavior questionnaire	Coaches		x		x	x
Injury-preventive coaching practices	Coaches		x			x

*Conducted with biweekly measurements through the season

Figure 1. Timeline of outcome assessments of #Utviklingsklar.

- Pre-study baseline coaches: 13.05.2024.-29.08.2024
- Pre-study baseline players: 26.08.2024- 17.11.2024
- Study in season coaches: 06.02.2025-02.03.2025
- Study in season players: week 42, 44, 46, 48, 50, 52 of 2024 and 2, 4, 6, 8, 10, 12, 14 of 2025. Players pilot tested their questionnaire during the recruitment phase, these data are not included in the data collection time periods.
- Study post-season coaches: 21.04.2025-07.05.2025

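### The confidence interval for the coach determinant effects leaves out any correlation of changes among coaches in the same club, and the model also gives up some precision from the baseline score

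*SAP*

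**What the plan says.** SAP 5.2.4, with the same structure for handball and football, puts baseline, mid-season and end-of-season scores into one model as responses: "A linear mixed model will be fitted to the data from all three time points". The fixed part has "fixed effects for intervention (intervention vs control), time point, intervention x time point interaction, and geographical region". That is six arm-by-time means plus region, so each arm has its own baseline mean. On the random part: "The model will include random intercepts for coaches nested within clubs". There is no club-by-time term and no clustered standard error. On the estimand, the handball plan says: "The effect measures will be the differences between the changes in aggregated behavioral determinant scores", at mid-season and at end of season against baseline; the football plan applies this to each determinant separately.

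By contrast, 5.2.3 (injury burden) and 5.2.5 (coaching practices, reported by coaches as a change) both correct their standard errors for clubs. Section 3.1 requires a 95% interval for every effectiveness estimate. Section 2.4.1 treats everything except the primary analysis as supportive.

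**The concern.** The e-learning course, workshop and club meeting (2.1) are undertaken by coaches and a leader of the same club. Coaches in one club may therefore change together, for instance because a meeting went well or badly or because a club plan was or was not adopted. That shared movement is between-club variation in change, and it belongs in the uncertainty of a club-randomised comparison. A random intercept for club describes clubs that are persistently high or low. It says nothing about clubs that move by different amounts, so the interval can be too narrow.

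Separately, an unconstrained difference in change gives the baseline score a weight of one, whatever its correlation with follow-up. With few coaches and ten determinants at two follow-up times, giving up precision has a cost. The SAP makes no precision calculation for these outcomes.

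**Working it through.** **Inputs from the SAP.** "With approximately 120 coaches, many of the categories will be sparsely populated" (5.2.5). "The target number of clubs to recruit is therefore 15 in each trial arm" (2.3), so 30 clubs and 120/30 = 4 coaches per club. "clubs will be randomly assigned to either the control or intervention group in a 1:1 allocation ratio" (2.2).

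**Inputs the SAP does not give, so assumed.** Correlation of changes between coaches in one club (c): 0 to 0.20. Correlation between two scores of the same coach (r): 0.3 to 0.8. Club ICC of the scores: 0 to 0.10.

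**The plan's own figure.** There is none for coach scores. The only sample size calculation concerns the player outcome: 196 per arm x (1 + 63 x 0.05) / 64 = 12.7, rounded up to the stated 13 clubs per arm. It does not bear on this point.

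**Step 1: why the intercepts cancel.** Write a coach's score as fixed part + club effect + coach effect + residual at that time. In follow-up minus baseline, the club and coach effects appear in both terms and drop out. What remains is the difference of two residuals, which the model takes as independent between coaches. With complete data this is exact. With missing scores it is approximate.

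**Step 2: size of the clustering error.** If changes in one club correlate at c, the true variance of the mean change is inflated by 1 + (4 - 1)c, and the model omits that factor. The ratio of model SE to true SE is 1/sqrt(1 + 3c). Approximate coverage of the nominal 95% interval is the normal probability within 1.96 times that ratio.

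| c (assumed) | 1 + 3c | Model SE / true SE | SE too small by | Approx. coverage |
|---|---|---|---|---|
| 0 | 1.00 | 1.00 | 0% | 95% |
| 0.05 | 1.15 | 0.93 | 7% | 93% |
| 0.10 | 1.30 | 0.88 | 12% | 91% |
| 0.20 | 1.60 | 0.79 | 21% | 88% |

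Simulation of the planned model (30 clubs, 4 coaches, 3 times) agrees: coverage 94.7%, 92.9%, 91.2% and 87.3%.

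**Step 3: precision given up at baseline.** With complete data and total variance 1, the planned difference in change has variance proportional to 2(1 - r). With one common baseline mean and no club effect it is 1 - r^2, so the ratio is (1 + r)/2. A club effect reduces the gain, so the variance was also computed by generalised least squares for 30 x 4 x 3 observations under the SAP's own random-intercept covariance, leaving region out. Entries are the variance with a common baseline mean divided by the variance of the planned model:

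| r (assumed) | Club ICC 0 | 0.05 | 0.10 |
|---|---|---|---|
| 0.3 | 0.65 | 0.70 | 0.73 |
| 0.5 | 0.75 | 0.78 | 0.81 |
| 0.7 | 0.85 | 0.87 | 0.88 |
| 0.8 | 0.90 | 0.91 | 0.92 |

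Interval width follows the square root. The gain runs from about 19% narrower (r = 0.3, ICC 0) to about 4% (r = 0.8, ICC 0.10), and is about 12% at r = 0.5 and ICC 0.05.

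**Step 4: what the planned model already takes from baseline.** At ICC 0.05, analysing follow-up scores alone would have 0.82, 0.96, 1.15, 1.92 and 2.88 times the variance of the planned model at r = 0.3, 0.4, 0.5, 0.7 and 0.8. At r = 0.5 the planned model therefore keeps (1.15 - 1)/(1.15 - 0.78), about 41%, of the attainable variance reduction; at r = 0.7 about 88% and at r = 0.8 about 96%. Only at r of about 0.4 or below is it less precise than ignoring baseline.

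**The case against.** **Clubs are already in the model.** A reader might infer either that 5.2.4 ignores clubs or that it contradicts 5.2.5. The SAP supports neither reading. Section 5.2.4 has a club random intercept, and 5.2.5 is an ordinary regression without random effects, so it needs clustered errors for its own reasons. What stands is narrower: the club intercept does not reach the contrast that is reported. A fair practical caution also remains, since a club-by-time variance may be poorly estimated from 30 clubs of about four coaches.

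**The size is assumed.** This is correct. The interval cannot be called wrong by any particular amount, and at zero correlation it is right.

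**The free baseline is defensible.** A reader might infer that the plan throws the baseline away. It does not, as Step 4 shows. The outcome is defined as change (5.1.3.2), and the model targets that without bias under randomisation. Moreover, a common baseline mean is safe in a cluster trial only if coach enrolment and baseline answers were not influenced by allocation. Clubs are randomised on enrolment (2.2), coaches are not blinded, and Figure 1 places randomisation and baseline in the same column without giving their order. The handball coach window is long: "Pre-study baseline coaches: 13.05.2024.-29.08.2024". If coach composition differed persistently between arms by d, the planned difference in change would remove d, whereas a common baseline mean would leave about (1 - r)d, or half of d at r = 0.5 with no club effect. This objection stands, and it makes the second part conditional.

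**Conclusion.** The point holds in two parts of unequal weight.

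The clustering part concerns the validity of the interval and does not depend on the order of baseline and randomisation. As specified, the 95% interval in 5.2.4 makes no allowance for correlated changes within clubs. The shortfall in the standard error is unknown from the SAP. It is about 7% to 21% if the correlation of changes is 0.05 to 0.20 with four coaches per club, and nil if that correlation is zero.

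The baseline part concerns efficiency only. Some precision is lost, worth about 4% to 19% of interval width over the assumed ranges. Those figures use the SAP's random-intercept covariance with complete data. The gain may be taken only if baseline is shown to be free of influence from allocation.

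Neither part biases the planned point estimate under randomisation, and neither touches the primary analysis. These are supportive outcomes, so the matter should be corrected but does not threaten the trial's main conclusion.

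**What to change.** In 5.2.4 of both SAPs:

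1. Add a club-by-time random effect, or use standard errors clustered on club as in 5.2.3 and 5.2.5, with a small-sample correction suited to about 30 clubs. Name the fallback if the club-by-time variance cannot be estimated.
2. State in 2.6 whether coaches were enrolled and their baseline scores recorded before allocation was known.
3. If it is confirmed that allocation affected neither, constrain the arms to one baseline mean: drop the intervention main effect, keep time, the two intervention-by-post-baseline terms, region and the random effects. Adjusting for the baseline score is an alternative. If this cannot be confirmed, keep the free baseline and make only the first change.

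The cost is a few sentences of SAP text and a few lines of code. No new data are needed.
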